6.2.3 Screening Period

The Screening Period starts when the subject signs and dates the informed consent form (ICF) and ends when the subject is enrolled/randomized, or screen failed. The Screening Period is up to 28 days. Certain initial Screening Period procedures may be repeated during the original initial Screening Period. Repeating procedures during the original initial Screening Period is a part of screening and is not considered “rescreening.” These procedures include laboratory assessments due to value(s) out of range due to a potential sampling error or that could be within range with repeat sampling.

6.2.4 Baseline

Baseline will be identified as the last non-missing assessment result taken prior to the date/time of the randomization/enrollment.

6.2.5 Treatment Period

Data collected on Day 1 will be assigned to the Treatment Period unless the time (HH:MM) of data collection and time (HH:MM) of randomization are both recorded, and the data collection time is before the time of randomization. In this case, the assessment will be assigned to the Screening Period.

If the time (HH:MM) of data collection is not recorded but the protocol and/or CRF includes an instruction to the effect that all Day 1 assessments are to be performed prior to randomization, the data collected at Day 1 will be assigned to the Screening Period. However, adverse events and concomitant

medications starting on Day 1, will be assigned to the Treatment Period, unless the time (HH:MM) demonstrates otherwise. Adverse events occurring within 4 weeks of the last dose of study drug will also be assigned to the Treatment Period. Adverse events occurring > 4 weeks after the last dose of study drug will be assigned to the “Safety Follow-up Period”.

The Treatment Period will be defined as the time from the date/time of randomization to 1 week after the last dose or when the subject completes their End of Treatment visit. Adverse events that occur within 4 weeks of the last dose of study drug will be attributed to the Treatment Period as well.

Treatment Period will also be divided into 2 periods, Period 1 and Period 2:

- Period 1 is the placebo-controlled period, and will start at the date of randomization and end at Week 16 when Week 16 assessments are completed and before administration of study drug in Period 2 (at or after Week 16 dose date/time). If a subject discontinues study drug prior to Week 16 and continues to attend visits without treatment through Week 16 (e.g. eCRF visit or analysis visit Week 8, Week 12, Week 16), then these visits’ results will be considered in Period 1, and should be included in efficacy/safety summaries.
- Period 2 will start at the time of first administration of study drug at or after Week 16 and end at Week 56 or early termination/end of treatment visit. If a subject discontinued study drug prior to Week 16 and continues to attend visits without treatment after Week 16 (e.g. eCRF visit or analysis visit Week 20, 24, etc.), then these visits’ results will be considered in Period 2 and should be included in efficacy/safety summaries.

The Safety Follow-up Period will start after completion of the End of Treatment visit (either Week 52 or EOT for subjects who discontinue treatment) or 8 days after the last dose of study drug (for subjects who don’t complete the End of Treatment visit). Adverse events that occur within 4 weeks of the last dose of treatment will not be assigned to the Safety Follow-up Period (rather, they will be assigned to the Treatment Period, either Period 1 or Period 2), but any adverse events after that time will be assigned to the Safety Follow-up Period. All other data collected in the defined Safety Follow-up Period will be assigned to it as stated.

6.3 Disposition of Subjects

Disposition categories are defined in [Table 3](#), below:

Table 3: Disposition Categories

Category	Definition
Study Disposition	
Completed Week 12 Assessment	Subject has a non-missing efficacy result at their Week 12 visit.
Completed Study at Week 12	Subject has a non-missing Week 12 analysis visit (includes windowed early termination/unscheduled visit results) or has any visit after Week 12.
Discontinued Study Before Week 12	Subject has Completed = “No” or status = “Discontinued” on the End of Study Form and missing Week 12 analysis visit (includes windowed early termination/unscheduled visit

	results) and has no additional results at visits after Week 12
Completed Week 16 Assessment	Subject has a non-missing efficacy result at their Week 16 visit.
Completed Study at Week 16 (Period 1)	Subject has a non-missing Week 16 analysis visit (includes windowed early termination/unscheduled visit results) or has any visit after Week 16.
Discontinued Study before Week 16 (within Period 1)	Subject has Completed = "No" on the End of Study Form and missing Week 16 analysis visit (includes windowed early termination/unscheduled visit results) and has no additional results at visits after Week 16.
Discontinued Study before Week 52 (within Period 2)	Subject has Completed = "No" on the End of Study Form and has at least 1 visit in Period 2 completed (includes windowed early termination/unscheduled visit results)
Completed Study at Week 52	Subject has a non-missing Week 52 analysis visit (includes eCRF visits and windowed early termination/unscheduled visit results) or has any visit after Week 52.
Discontinued Study any time before Week 52	Subject has Completed = "No" on the End of Study Form and missing Week 52 analysis visit (includes windowed early termination/unscheduled visit results) and has no additional results at visits after Week 16.
Completed Study	Subject has Completed = "Yes" on the End of Study Form
Discontinued Study	Subject has Completed = "No" on the End of Study Form
Treatment Disposition	
Completed Treatment Through Week 11	At least one dose of study drug has been administered on or after Week 11
Discontinued Treatment Prior to Week 11	Completed = "No" on the End of Treatment form and no dose administered on or after Week 11.
Completed Treatment Through Week 15 (Period 1)	A dose of study drug has been administered on or after Week 15
Discontinued Treatment before Week 15 (within Period 1)	Completed = "No" on the End of Treatment form and no dose administered on or after Week 15.
Discontinued Treatment before Week 51 (within Period 2)	Completed = "No" on the End of Treatment form and at least one dose of study drug administered in Period 2
Completed Treatment through Week 51	Completed = "Yes" on the End of Treatment Form
Discontinued Treatment any time before Week 51	Completed = "No" on the End of Treatment form

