2. INTRODUCTION

This study will be conducted to evaluate the efficacy and safety of izokibep in the treatment of subjects with moderate to severe Hidradenitis Suppurativa (HS). Izokibep is a small protein molecule that acts as a selective, potent inhibitor of Interleukin (IL) 17A, to which it binds with high affinity.

This study investigates izokibep in subjects with active HS, including tumor necrosis factor-alpha inhibitor (TNFi) naïve subjects, and those who had an inadequate response or intolerance to TNFi, or for whom TNFi is contraindicated. The study is intended to be 1 of 2 adequate and well-controlled studies to support a claim of efficacy of izokibep in subjects with HS. Hidradenitis suppurativa clinical response 75 (HiSCR75) at Week 12 will be utilized to compare izokibep to placebo, for the primary endpoint.

This statistical analysis plan (SAP) will define the final analyses planned for the study.

The study will be terminated early after all subjects completed (or discontinued) treatment at Week 32. A decision was made to write an abbreviated clinical study report (CSR). The analyses described thereafter reflect this decision.

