6.2.2 Visit and Timepoint Windows

In general, data will be analyzed using the nominal study visits as defined in the SoA in the protocol and reported on the eCRF.

If a subject discontinues the study early, the subject will have an early termination visit which includes efficacy and safety assessments. If the early termination visit occurs in a timeframe that corresponds to a scheduled efficacy or safety assessment (week 2, 4, 8, 12, 16, 20, 24, 32, or 52), and if the subject does not have an actual visit at or after the corresponding scheduled efficacy or safety assessment, the day ranges below will be used to map the early termination visit to a scheduled efficacy assessment for use in all efficacy summaries at that timepoint.

In addition, unscheduled visit results will not be included in analyses, unless the unscheduled visit corresponds to a nominal visit for which the result is missing or if the unscheduled visit is selected as baseline. If the nominal visit result is missing, then the unscheduled visit result will also be mapped according to the ranges in Table 1 and Table 2 below for efficacy and safety assessments, respectively. If multiple unscheduled visits fall into 1 analysis window, then the one closest to the scheduled day will be used for analysis. If the 2 unscheduled visits are equidistant from the scheduled day, the later assessment will be used.

Table 1: Visit Windowing for Efficacy Assessments

Nominal Visit	Scheduled Day	Analysis Window (Relative Days)
Day 1/Week 0 (Baseline)	1	[1, 1]
Week 2	14	[2, 21]
Week 4	28	[22, 42]
Week 8	56	[43, 70]
Week 12	84	[71, 98]
Week 16	112	[99, 140]
Week 24	168	[141, 196]
Week 32	224	[197, 294]
Week 52	364	[295, later]

Table 2: Visit Windowing for Safety Assessments:

Nominal Visit	Scheduled Day	Analysis Window (Relative Days)
Day 1/Week 0 (Baseline)	1	[1, 1]
Week 2	14	[2, 21]
Week 4	28	[22, 42]
Week 8	56	[43, 70]
Week 12	84	[71, 98]
Week 16	112	[99, 126]
Week 20	140	[127, 154]
Week 24	168	[155, 196]
Week 32	224	[197, 294]
Week 52	364	[295, later]

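### SAP Table 3 labels subjects who exit before Week 12, 16 or 52 as completers of that timepoint, and its Week 52 rows overlap and omit leavers

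*SAP*

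**What the plan says.** SAP Section 6.2.2 explains what happens to an early-termination visit when the subject has no actual visit at or after the scheduled one: "the day ranges below will be used to map the early termination visit to a scheduled efficacy assessment for use in all efficacy summaries". In Table 1 the Week 12 window is Days 71 to 98, Week 16 is Days 99 to 140, and Week 52 is Day 295 onwards. The safety windows in Table 2 have the same three lower limits.

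Table 3 in Section 6.3 then uses the mapped visit to define study completion:

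- For Week 12, this is the test: "Subject has a non-missing Week 12 analysis visit (includes windowed early termination/unscheduled visit results) or has any visit after Week 12".
- For Week 16, this is the test: "Subject has a non-missing Week 16 analysis visit (includes windowed early termination/unscheduled visit results) or has any visit after Week 16".
- For Week 52, this is the test: "Subject has a non-missing Week 52 analysis visit (includes eCRF visits and windowed early termination/unscheduled visit results) or has any visit after Week 52".

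The Week 12 discontinuation row needs the End of Study form to show non-completion, nothing at later visits, and no windowed visit; the SAP's wording is "and missing Week 12 analysis visit (includes windowed early termination/unscheduled visit". The Week 16 row is built the same way. The row for discontinuation before Week 52 within Period 2 has a different test: not completed "on the End of Study Form and has at least 1 visit in Period 2 completed". It does not ask for the Week 52 visit to be missing. The row for discontinuation at any time before Week 52 does ask for that, and also for no results at visits after Week 16.

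The overall *Completed Study* and *Discontinued Study* rows come from the End of Study form alone. Section 9.1 tabulates these rows by treatment group, with reasons for discontinuation.

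**The concern.** A row headed as completing the study at Week 12 will be read as retention to the primary timepoint. Under Table 3 it also includes people who left before that timepoint but attended an exit visit inside the efficacy window. Data availability has its own row, *Completed Week 12 Assessment*. Subtracting one row from the other does not recover the early leavers, because the difference also contains subjects who missed Week 12 and came back later.

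Retention matters in this programme. The protocol's summary of changes gives dropout among responders in Study 21102 as one of two reasons for moving the primary endpoint from Week 16 to Week 12; the other is the high placebo response. This SAP also drops the sensitivity analyses of the primary endpoint (Section 9.5.1) and the protocol-deviation summaries (Section 9.2). Disposition by arm is therefore one of the main remaining views of missingness. The tabulation of imputed subjects in Section 9.5 does not fill the gap: a windowed exit visit counts as observed Week 12 data, so its subject is not there as missing.

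**Working it through.** The plan states no retention figure to reproduce. The inputs are the scheduled days and window limits in SAP Tables 1 and 2, and the visit tolerances in Protocol Section 1.3 (±3 days for treatment visits, ±5 days for Week 52).

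**How early an exit can be and still count** (scheduled day minus lower window limit):

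| Timepoint | Scheduled day | Lower limit | Gap | Exit days mislabelled | Protocol tolerance |
|---|---|---|---|---|---|
| Week 12 | 84 | 71 | 84 − 71 = 13 days | 71–83 | 3 days |
| Week 16 | 112 | 99 | 112 − 99 = 13 days | 99–111 | 3 days |
| Week 52 | 364 | 295 | 364 − 295 = 69 days | 295–363 | 5 days |

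If Day 1 is taken as Week 0, the scheduled days become 85, 113 and 365, and the gaps 14, 14 and 70 days.

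**Week 12 example.** The protocol places the early-termination visit 1 week after the last dose. An exit visit on Day 71 implies a last dose near Day 71 − 7 = 64. The Week 12 analysis visit is not missing, so the subject is a Week 12 completer and fails the test for discontinuation before Week 12.

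**Week 52 example.** Take an exit visit on Day 300, with the End of Study form showing non-completion.

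- *Completed Study at Week 52*: met, since Day 300 lies in the window.
- *Discontinued Study before Week 52 (within Period 2)*: met, since the form says no and a Period 2 visit exists.
- *Discontinued Study any time before Week 52*: not met, since the Week 52 analysis visit is present.

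Now take an exit on Day 200. The Week 52 visit is missing and the Period 2 row is met. The any-time row still fails, because the subject has results after Week 16. Most Period 2 leavers will have such results, so the any-time row can be smaller than the Period 2 row that should be a subset of it.

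**A second route.** The rows also accept any later visit, and Table 3 does not say whether the safety follow-up, due 8 weeks (56 days) after the last dose, is one. If it is, a last dose just after Day 84 − 56 = 28 could make a subject a Week 12 completer.

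**Illustrative size at Week 12.** Assume that 15% leave before Week 12, evenly over 84 days, and that all attend an exit visit. Leavers per arm: 0.15 × 125 = 18.75, about 19.

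- Exits on Days 71–83: 13/84 = 15.5%; 18.75 × 13/84 = 2.9 subjects; reported dropout 15% × (1 − 13/84) = 12.7%.
- Treating Days 81–83 as within the protocol's tolerance, exits on Days 71–80: 10/84 = 11.9%; 18.75 × 10/84 = 2.2 subjects; reported dropout 13.2%.

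**The case against.** The strongest reply is that the information survives elsewhere. The Day 71 leaver still appears by arm in the overall discontinued row with a reason, in treatment discontinuation before Week 11 with a reason, and in the day-of-discontinuation categories of Section 9.1. If the safety follow-up does not count as a later visit, that subject is also in the row for discontinuation before Week 16. A reader might infer that the reason for leaving disappears from the report. It does not; it is missing only from the row for the timepoint concerned. This part of the reply stands.

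A reader might also infer that a large share of subjects will be called Week 52 completers because of the sponsor's stop. With uniform enrolment over 20 to 40 weeks, and everyone continuing until the last subject reached Week 32, the share with a last visit in Weeks 42 to 52 would be 10/20 = 50% down to 10/40 = 25%, ignoring dropout. The documents give no enrolment period. The SAP's sentence, "The study will be terminated early after all subjects completed (or discontinued) treatment at Week 32", can also mean that each subject ended at Week 32, in which case only those already past that point could reach Day 295. These percentages are not supported.

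It is also fair that the Week 12 illustration is near the upper end. The 15% is assumed, and the protocol asks for exit visits only where possible.

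Finally, the rows can be read as following the SAP's analysis-visit convention. That explains how the rule arose. It does not make a Day 71 exit a completion of Week 12, or reconcile the Week 52 rows.

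**Conclusion.** The definitions are wrong as written. They label early leavers as completers at all three timepoints, remove them from the paired discontinuation rows at Weeks 12 and 16, and leave the Week 52 rows overlapping and incomplete. The day gaps follow directly from the SAP's own tables.

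The effect is on reported retention by arm, and its size cannot be computed from the documents because they give no exit-visit days. The figure of 2 to 3 of about 19 leavers per arm at Week 12 rests on 15% uniform dropout and full exit-visit attendance.

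A reader might take this as a flaw in the primary analysis. It is not: no test, estimand or imputation rule uses Table 3. The use of windowed visits as Week 12 efficacy data comes from Section 6.2.2 and is a separate matter.

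**What to change.** In SAP Table 3:

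1. Count a subject as having completed the study at Week X only if they attended the nominal Week X visit or a later scheduled treatment-period visit, or had an early-termination or unscheduled visit on or after the lower limit of the protocol visit window. On the SAP's scheduled days that limit is 84 − 3 = Day 81, 112 − 3 = Day 109, and 364 − 5 = Day 359. At Week 52, an end-of-treatment visit before Day 359 should not count.
2. State that the safety follow-up visit is not a later visit for this purpose.
3. Define each discontinued row as the complement of its completed row, using End of Study status and date, so that the two are mutually exclusive. This includes the Period 2 row.
4. In the row for discontinuation at any time before Week 52, change the reference to visits after Week 16 to visits after Week 52.
5. Keep the Table 1 windows for efficacy only.

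A cutoff is better than barring every windowed visit: a subject who exits on Day 90 was in the study through Week 12 and should remain a completer. The cost is SAP wording and a few reprogrammed disposition rows, with slightly lower reported completion.

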6.4 Protocol Deviations

Protocol deviations will be determined outside of the eCRF. The protocol deviations review will include a determination of which deviations are identified as important. Representatives from ACELYRIN, INC. will participate in the review of the deviations.

6.5 Demographics and Baseline Characteristics

The following assessments will be collected at baseline:

- Demographic parameters
 - Age (years) at Screening
 - Sex
 - Race
 - Ethnicity
- Vital Signs
 - Height (centimeters [cm])
 - Weight (kilograms [kg])
 - Body Mass Index (BMI; kg/m²) – calculated using the following formula: *Weight (kg) ÷ (Height (cm)/100)²*
 - Body Temperature (Celsius [C]) – temperatures collected in Fahrenheit will be converted to C using the following formula: *(temperature in Fahrenheit – 32) x 5/9*
 - Respiratory Rate (breaths per minute)
 - Systolic Blood Pressure (SBP [mmHg])
 - Diastolic Blood Pressure (DBP [mmHg])
 - Heart Rate (beats per minute [bpm])
- Disease Characteristics
 - Time since diagnosis with HS (years) – calculated using the following formula: *(date ICF signed – date of diagnosis + 1)/365.25*
 - *If the date of diagnosis is incomplete, a date based on the same logic as used for concomitant medications and adverse events (described in Section 8.3) will be imputed*
 - AN Count
 - Abscess Count
 - Draining Fistula Count
 - Non-Draining Fistula Count
 - Total Fistula Count – calculated using the following formula:
 - *draining count + non-draining count*
 - Inflammatory Nodule Count
 - Non-inflammatory Nodule Count
 - Hurley Stage (II, III)
 - Location of lesions
- Other Baseline Characteristics
 - HADS Total Score
 - HADS-Anxiety
 - HADS-Depression
 - PGA Assessment

- DLQI Score
- EQ-5D (Domain Scores [Mobility, Self-Care, Pain/Discomfort, Usual Activities, and Anxiety/Depression], Index Score, Visual Analog Scale (VAS) Score)
- SF -12 (Mental Component Score and Physical Component Score)
- Columbia-Suicide Severity Rating Scale (C-SSRS)
- NRS Pain Score (At its Worst and On Average)
- IHS4
- HiSQOL
- Childbearing potential (Yes, No)
- Alcohol Use (Never, Current, Former)
- Nicotine Use (Never, Current, Former)
- Medical History
 - Medical history is defined as any condition, apart from the study indication, that the subject may have prior to enrollment in the study. Medical occurrences that begin before the start of study drug administration, but after obtaining ICF will be recorded as medical history/current medical conditions, not as AEs. The only exception to this rule is for serious adverse events – these are collected as such starting from the date of obtaining ICF.
 - Medical history will be coded using the latest Medical Dictionary for Regulatory Activities (MedDRA) version around the time of Database Lock.

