#### Type of Subject and Disease Characteristics

3. Diagnosis of HS for  $\geq$  6 months prior to first dose of study drug.
4. Hidradenitis suppurativa lesions present in  $\geq$  2 distinct anatomic areas (eg, left and right axilla; or left axilla and left inguino-crural fold), one of which is Hurley Stage II or Hurley Stage III at screening and Day 1 prior to enrollment/randomization.
5. A total AN count of  $\geq$  5 at screening and Day 1 prior to enrollment/randomization.
6. Subject must have had an inadequate response to oral antibiotics (defined as  $\geq$  3-month treatment with an oral antibiotic for treatment of HS) OR exhibited recurrence after discontinuation to, OR demonstrated intolerance to, OR have a contraindication to oral antibiotics for treatment of their HS as assessed by the investigator through subject interview and review of medical history.
7. Must agree to use daily or a minimum of 3 days a week (throughout the duration of the study) one of the following over-the-counter topical antiseptics on their body areas affected with HS lesions: chlorhexidine gluconate, triclosan, benzoyl peroxide, diluted bleach in bathwater, or as otherwise determined acceptable by ACELYRIN medical monitor.
8. Subject must be willing to complete a daily skin pain diary 7 consecutive days prior to Day 1; if skin pain diaries are not completed for at least 3 of the 7 consecutive days prior to the Day 1 visit, the subject may not be enrolled/randomized.

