### **8.1.10. Short Form 12**

The acute Short Form-12v2™ Health Survey (SF-12v2) is a 7-day recall, 12-item subset of the Short Form-36v2™ questionnaire that measures the same 8 domains of health including physical functioning, role-function, bodily pain, general health, vitality, social functioning, role-emotional, and mental health. The SF-12 is a brief, reliable measure of overall health status with scores general for physical component and mental components. Each item on the SF-12 is score on 3- or 5-item Likert scales and the domains scales are standardized to 0 to 100 scale where 0 represents lower quality of life and 100 represents higher quality of life. The subject should complete the questionnaire before site personnel performs any clinic assessments and before any interaction with the site personnel has occurred to avoid biasing the subject's response.

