8.3 Handling of Dropouts or Missing Data

When considering AE and Concomitant Medications, partial start/end dates will be handled in a conservative fashion so that if there is any possibility that the available partial information could reasonably result in the AE being treatment-emergent or the medication being concomitant, that it will be imputed as such. Specifically:

- If the start day is missing but month and year are present:
 - o If the known month/year are the same as the month/year of the first dose of treatment, then impute to the date of the first dose of treatment;
 - o Otherwise, impute the day to 01.
- If the start day and month are both missing but the start year is present:
 - o If the known year is the same as the year of the first dose of treatment, then impute to the date of the first dose of treatment;
 - o Otherwise, impute the day and month to 01January.
- If the start date is completely missing, impute to the date of the first dose of treatment, unless the end date suggests it could have started prior to this, in which case impute to 01January of the same year as the end date.
- When imputing a start date, ensure that the new imputed date is on or prior to the end date of the AE or medication.
- If the end date is missing or partial, and the AE/medication is not ongoing (i.e. for AE, the outcome is not “Recovering/Resolving”, “Not Recovered/Not Resolved”, or “Unknown”), then impute the missing/partial end date as follows:
 - o If the end day is missing but month and year are present:
 - If the known month/year are the same as the month/year of the first dose of treatment, then impute to the date of the first dose of treatment;
 - Otherwise, impute the day to the last day of the month.
 - o If the end day and month are both missing but the end year is present:
 - If the known year is the same as the year of the first dose of treatment, then impute to the date of the first dose of treatment;
 - Otherwise, impute the day and month to 31December.
 - o If the end date is completely missing, impute to the date of the first dose of treatment.
 - o When imputing an end date, ensure that the new imputed date is on or after the start date of the AE or medication.
- Other unexpected combinations of partial date information (e.g., known month but missing day and year) will be handled as needed on a case-by-case basis.

The handling of missing efficacy data will be discussed throughout sections 6 and 9.

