13.1.8 Hidradenitis Suppurativa – Physician Global Assessment (HS-PGA)

Although this value is collected directly on the eCRF, for analysis purposes it will be derived programmatically due to inconsistent and unreliable entry on the eCRF.

Derivation will be as follows:

- Clear: No inflammatory or non-inflammatory nodules
- Minimal: Only the presence of non-inflammatory nodules
- Mild: [< 5 inflammatory nodules and no abscess/draining fistula] or [(1 abscess or 1 draining fistula) and no inflammatory nodules]
- Moderate: [≥ 5 inflammatory nodules and no abscess/draining fistula] or [(1 abscess or 1 draining fistula) and ≥ 1 inflammatory nodules] or [(2 to 5 abscesses or 2-5 draining fistulas) and (< 10 inflammatory nodules)]
- Severe: [2 to 5 abscesses or 2 to 5 draining fistulas] and ≥ 10 or more inflammatory nodules
- Very severe: > 5 abscesses or draining fistulas

The derivation above follows [Table 11](#) from (Daoud Mathieu, 2023):

Table 11: HS-PGA Scoring

	Abscesses + draining fistulas	Inflammatory nodules	Non-inflammatory nodules
Clear (1)	0	0	0
Minimal (2)	0	0	>0
Mild (3)	0	1 - 4	
	1	0	
Moderate (4)	0	≥ 5	
	1	≥ 1	
	2 - 5	< 10	
Severe (5)	2 - 5	≥ 10	
Very Severe (6)	> 5		

If the count of abscesses, draining fistulas, or non-inflammatory nodules is missing for a region, then the HS-PGA score will not be calculated.

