SF-12v2 scale	Sum final Item Values (after recoding items)	Lowest and highest possible raw scores	Possible raw score range
Physical Functioning (PF)	Items 2a + 2b	2, 6	4
Role Physical (RP)	Items 3a + 3b	2, 10	8
Bodily Pain (BP)	Item 5	1, 5	4
General Health (GH)	Item 1	1, 5	4
Vitality (VT)	Item 6b	1, 5	4
Social Functioning (SF)	Item 7	1, 5	4
Role Emotional (RE)	Items 4a + 4b	2, 10	8
Mental Health (MH)	Items 6a + 6c	2, 10	8

Standardization of SF-12v2 scales (Z-scores), Standard Form:

Formulas for z-score standardization of SF-12v2 scales, Standard Form:

SF-12v2	Z-scores
Physical Functioning (PF_Z)	PF_Z = (PF - 81.18122) / 29.10558
Role Physical (RP_Z)	RP_Z = (RP - 80.52856) / 27.13526
Bodily Pain (BP_Z)	BP_Z = (BP - 81.74015) / 24.53019
General Health (GH_Z)	GH_Z = (GH - 72.19795) / 23.19041
Vitality (VT_Z)	VT_Z = (VT - 55.59090) / 24.84380
Social Functioning (SF_Z)	SF_Z = (SF - 83.73973) / 24.75775
Role Emotional (RE_Z)	RE_Z = (RE - 86.41051) / 22.35543
Mental Health (MH_Z)	MH_Z = (MH - 70.18217) / 20.50597

Norm-Based Transformation of SF-12v2 scales Z-scores, Standard Form:

SF-12v2	Norm-Based scores
Physical Functioning (Norm-Based PF)	Norm-Based PF = 50 + (PF_Z * 10)
Role Physical (Norm-Based RP)	Norm-Based RP = 50 + (RP_Z * 10)
Bodily Pain (Norm-Based BP)	Norm-Based BP = 50 + (BP_Z * 10)
General Health (Norm-Based GH)	Norm-Based GH = 50 + (GH_Z * 10)
Vitality (Norm-Based VT)	Norm-Based VT = 50 + (VT_Z * 10)

Social Functioning (Norm-Based SF)	Norm-Based SF = 50 + (SF_Z * 10)
Role Emotional (Norm-Based RE)	Norm-Based RE = 50 + (RE_Z * 10)
Mental Health (Norm-Based MH)	Norm-Based MH = 50 + (MH_Z * 10)

2. Norm-Based Scoring SF-12v2 Physical and Mental Summary Measures (Standard 4-week recall)

SF-12v2	Aggregated scores
Aggregate Physical Summary Score (AGG_PHYS)	AGG_PHYS = (PF_Z * 0.42402) + (RP_Z * 0.35119) + (BP_Z * 0.31754) + (GH_Z * 0.24954) + (VT_Z * 0.02877) + (SF_Z * -0.00753) + (RE_Z * -0.19206) + (MH_Z * -0.22069)
Aggregate Mental Summary Score (AGG_MENT)	AGG_MENT = (PF_Z * -0.22999) + (RP_Z * -0.12329) + (BP_Z * 0.09731) + (GH_Z * -0.01571) + (VT_Z * 0.23534) + (SF_Z * 0.26876) + (RE_Z * 0.43407) + (MH_Z * 0.48581)

3. Transformation of Summary Scores (Standard Form)

SF-12v2	Z-scores
Transformed Physical Component Score (PCS)	50 + (AGG_PHYS * 10)
Transformed Mental Component Score (MCS)	50 + (AGG_MENT * 10)

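### Time since diagnosis and HS-PGA are wrongly specified for the baseline table, and the SF-12v2 scoring form does not match the form administered

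*SAP*

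**What the plan says.** **Time since diagnosis.** SAP 6.5 computes it in years as ("date ICF signed – date of diagnosis + 1)/365.25". For incomplete dates it adds: "If the date of diagnosis is incomplete, a date based on the same logic as used for concomitant medications and adverse events" is to be imputed, with a pointer to SAP 8.3. Section 8.3 is built so that doubtful adverse events count as treatment-emergent and doubtful medications as concomitant. For a year-only date its test is "If the known year is the same as the year of the first dose of treatment"; if so, the first-dose date is used, otherwise 1 January. With only the day missing, it uses the first-dose date if the month and year match first dose, otherwise day 01. For no date at all: "If the start date is completely missing, impute to the date of the first dose of treatment". Protocol 5.1, criterion 3, requires diagnosis at least "6 months prior to first dose of study drug".

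**SF-12v2.** Protocol 8.1.10 describes the acute form, which "is a 7-day recall, 12-item subset of the Short Form-36v2". SAP 13.1.10 labels its z-score constants as Standard Form and heads the summary step "Norm-Based Scoring SF-12v2 Physical and Mental Summary Measures (Standard 4-week recall").

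**HS-PGA.** SAP 13.1.8 replaces the eCRF value with a programmed grade because entry was unreliable. It gives the grades in text and says the text follows Table 11. The lesion column of that table is "Abscesses + draining fistulas". The text instead tests abscesses and draining fistulas one against the other, joined by *or*.

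SAP 9.3 keeps all three variables in the baseline table for the full analysis set.

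**The concern.** The date rules in SAP 8.3 suit events that might have begun on treatment: where there is doubt, they move the start to first dose. A diagnosis must precede first dose by months, so for some missing-date patterns the same rules give a value that cannot be true. Because duration is counted back from consent, which normally comes before dosing, it can be negative.

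For HS-PGA, the text and the table are two specifications of one variable. Programmers working from one or the other would grade the same subject differently, and the eCRF grade is no longer there as a fallback.

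For SF-12v2, the protocol and the SAP name different recall forms of the instrument, so at least one is wrong.

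At stake is the description of who was studied: disease duration, physician-graded severity, and physical and mental health scores by arm.

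**Working it through.** The plan states no figure for these rules, so there is none to reproduce. The rules were applied as written.

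**(a) Time since diagnosis**

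Inputs: the SAP 6.5 formula, the SAP 8.3 start-date rules, and a screening period of up to 28 days (SAP 6.2.3). Let g be the days from consent to first dose. If the imputed diagnosis date is the first-dose date, then consent − diagnosis = −g, and duration = (1 − g)/365.25 years.

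| g (days) | duration (years) |
|---|---|
| 0 | +0.0027 |
| 1 | 0 |
| 2 | −0.0027 |
| 7 | −0.0164 |
| 28 | −0.0739 |

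The result is negative for any gap of 2 days or more.

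Worked case: first dose 16 Sep 2024, consent 28 days earlier (19 Aug 2024), only the year 2024 known. The rule gives −27/365.25 = −0.074 years. True dates that meet criterion 3 run from 1 Jan to 16 Mar 2024:
- from 16 Mar: (156 + 1)/365.25 = 0.43 years
- from 1 Jan: (231 + 1)/365.25 = 0.64 years

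Reach of the rule:
- Year-only date in the dosing year: an eligible subject needs a first dose in about July or later.
- Same month and year as first dose: cannot occur in an eligible subject.
- Other partial dates: day 01 or 1 January, the earliest possible date. Duration is positive and, if anything, too long, by up to about a month or a year.
- The 8.3 check against the end date gives no protection, because a diagnosis has no end date.

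**(b) SF-12v2**

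The protocol has the acute form with 7-day recall; the SAP has the Standard Form with 4-week recall. The documents contain no acute-form constants, so the error cannot be computed. The sensitivity can be shown under an assumption. Each summary score is 50 + 10 × Σ wₖ(scoreₖ − meanₖ)/SDₖ. With the SAP's weights and SDs held fixed, moving all eight means by δ moves the score by 10δ × Σ(wₖ/SDₖ) in size:
- δ = 1: physical 0.33, mental 0.54
- δ = 5: physical 1.64, mental 2.71

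The values of δ are assumed and are not estimates of the actual difference.

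**(c) HS-PGA**

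| Abscesses, fistulas, inflammatory nodules | Text | Table 11 |
|---|---|---|
| 1, 1, 12 | Moderate (one lesion of a type with at least one nodule; Severe needs 2 to 5 of one type) | Severe (sum 2, at least 10 nodules) |
| 5, 0, 0, and no non-inflammatory nodules | Clear (no nodules of either kind) and also Moderate (2 to 5 abscesses, under 10 nodules) | Moderate (sum 5) |

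Both profiles meet the entry requirement of an AN count of at least 5 (13 and 5).

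Text and table were then compared over abscesses 0–10, fistulas 0–10, inflammatory nodules 0–20 and non-inflammatory nodules 0 or 1, keeping AN ≥ 5: 4,752 profiles. The Very severe line (more than 5) can be read per lesion type or as a combined count.

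| Reading of more than 5 | Same single grade | Text gives several grades | Text gives one different grade |
|---|---|---|---|
| Per type | 1,977 | 2,213 | 562 |
| Combined | 1,977 | 2,753 | 22 |

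These count rule combinations, not expected patients.

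The missing-data sentence in 13.1.8 names abscesses, draining fistulas and non-inflammatory nodules. It leaves out inflammatory nodules, the count that separates Moderate from Severe.

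**The case against.** The strongest reply is that little depends on these items, and that parts of the criticism are easily overstated.

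- *Disease duration is understated generally.* A reader might infer this from the first-dose rule. The documents do not support it: only two branches shorten duration, and the rest lengthen it.
- *A wholly missing date may fall outside the rule.* SAP 6.5 speaks of incomplete dates, and 8.3 treats partial and completely missing dates separately. A site should also know enough to confirm criterion 3. This is fair. If it is accepted, only the year-only branch remains, and that branch still gives impossible values.
- *The SF-12v2 scores are wrong.* The documents prove a contradiction of form. They do not show that the acute-form constants differ from those printed, or by how much.
- *3 abscesses, 3 fistulas and 5 nodules is Moderate by the text and Very severe by the table.* This holds only if more than 5 is read per type. On the combined reading the text gives both grades. The 1, 1, 12 profile does not depend on that choice.
- *A programmer would simply use Table 11.* That is possible, since the SAP says the text follows it, but the text is also presented as the derivation.
- *Severity and quality of life are described elsewhere.* True: SAP 9.3 also reports lesion counts, Hurley stage, IHS4, DLQI, EQ-5D and HiSQOL.

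What survives is two rules that yield wrong or conflicting values and one unreconciled form.

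**Conclusion.** Time since diagnosis and HS-PGA are wrong as written; SF-12v2 is inconsistent between the documents.

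- Time since diagnosis: +0.003 to −0.074 years in the two affected branches, for a 0 to 28 day gap. The minimum of about 0.5 years runs to first dose; counted to consent 28 days earlier it is about 0.42 years. The number of subjects affected is unknown. The 28-day limit may be exceeded, because Protocol 6.3.2 and 10.1.3 waive a new consent when rescreening falls within 30 days.
- HS-PGA: text and table assign different grades to profiles that eligible subjects can have, on either reading of the Very severe line. How often such profiles occur is unknown. This assumes that the PGA entry in SAP 9.3 is the derived grade, as 13.1.8 implies.
- SF-12v2: the mismatch is certain; the size of any error cannot be determined from the documents.

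A reader might infer that efficacy conclusions are at risk. They are not: none of the three variables enters a hypothesis test (SAP 8.6) or the imputation model (SAP 9.5), and post-baseline HS-PGA and SF-12v2 analyses are dropped (SAP 5 and 9.7). The effect is limited to baseline description, so this is a minor correction.

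**What to change.** - **Diagnosis date.** Remove the pointer from SAP 6.5 to 8.3 and state a separate rule: no imputed date later than criterion 3 allows, and wholly missing dates left missing. Report how many dates were imputed or missing, so that a rule tied to eligibility is visible to the reader.
- **SF-12v2.** Confirm from the questionnaire actually used which recall form was given. If it was the acute form, score it from that form's manual; if it was the 4-week form, correct Protocol 8.1.10.
- **HS-PGA.** Define the grade from the Table 11 sum with mutually exclusive categories, including a zero abscess-plus-fistula condition for Clear. Set the grade to missing if any of the four counts (abscesses, draining fistulas, inflammatory nodules, non-inflammatory nodules) is missing.

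The cost is SAP wording and minor reprogramming of baseline variables. No new data are needed beyond checking the SF-12v2 form.
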